4.5.1 Dose Delivery Times

It is anticipated that a dose of study medication will take 2 to 6 minutes to be delivered, depending on the patient's inhalation/exhalation breathing pattern.

4.5.2 Packaging and Labelling

CCI
CCI
[REDACTED]

4.6 Preparation, Handling and Dispensing

4.6.1 Preparation Time

The study medication will not require reconstitution and will be supplied in pre-labelled syringes. Study medication will be put into the **CCI** nebuliser immediately prior to dosing.

4.6.2 Timing of Doses

The study medication should be taken once daily at approximately the same time of day. There must be a gap of at least 8 hours between doses (see Section 4.9 for the treatment of overdose).

4.6.3 Missed or Incomplete Doses

If a dose is missed or the complete dose is not taken, the following procedure must be followed:

1. Record in the source document and the eCRF that the dose has been missed/not completed with the reason why.
2. Continue with any remaining doses as normal (see Section 5.5 for patient withdrawal criteria).

4.7 Storage of Study Medication

Prior to dispensing, the study medication should be stored in a locked and temperature-controlled environment. The study medication should be stored between +2°C and +8°C. A daily temperature log must be kept to ensure that the study medication storage temperature is recorded. Any deviations from the storage conditions should be reported immediately to the Sponsor/Clinical Research Associate (CRA), and the study medication should be placed in quarantine and not used until authorisation has been given by the Sponsor to do so.

Patients who are discharged from hospital during the 14-day treatment phase should be instructed to keep the study medication in a refrigerator. Due to the stability data for the IMP, it is not necessary to keep a record of the fridge storage temperature at the patient's home.

Training will be given to the patients by study staff regarding storage of study medication, disposal of the syringes after they have been used to fill the device, what to do once they have completed all doses and any drug accountability that needs to be completed by the patient.

The study medication can be transported to the patient's home without the need for refrigeration. On arrival at the patient's home, the study medication should be placed in the refrigerator as soon as possible.

4.8 Drug Accountability

The Sponsor will provide the required documentation for study medication accountability, including reconciliation of drugs and maintenance of drug records.

The Investigator must maintain study medication accountability throughout the course of the study in accordance with regulatory requirements.

All patients who take the study medication whilst at home will either be asked to complete a drug accountability form after each dose of study medication or will be asked questions regarding it by study staff during their daily contact.

The amount of study medication received and dispensed to patients should be documented. Study medication dispensed to a patient should not be returned if unused. Patients will be given instructions for its disposal.

Drug accountability records will include:

- Confirmation and inventory of study medication delivery to the study site.
- An inventory of the study medication that has been provided to each patient.
- The serial number from the controller component of the **CCI** nebuliser device.
- Confirmation of administration of each dose of study medication.
- The return to the Sponsor or alternative disposition of unused products.

Dates of use, expiry dates, quantities, batch numbers, and the patient's randomisation and unique patient identification number should also be included on the accountability form.

Unused study medication must not be discarded without authority from the Sponsor or used for any purpose other than the present study.

During the study, where possible due to the nature of the study, the Sponsor (or delegate) will periodically review the drug accountability forms and check these against the actual study medication. Once the study has finished and the drug accountability forms have had a final check, the Sponsor (or delegate) will make arrangements for the return of the study medication or will authorise their destruction by the study site.

4.9 Treatment of Overdose

An overdose is defined as any dose greater than the once-a-day dose that is being used in this study i.e. two doses taken less than 8 hours apart. Any overdose must be recorded as a protocol deviation in the source documents.

In the event of overdose, if the patient is not in hospital, hospitalisation should be considered (if applicable) for observation and appropriate supportive treatment should be given. If the patient is in hospital, they should be observed and appropriate supportive treatment should be given. The Sponsor (or delegate) should be contacted in an expedient manner, whether associated with an AE (serious or non-serious) or not, to decide if the patient should continue in the study.

If the patient is experiencing AEs that may relate to an overdose of study medication, the IB should be consulted for details of any specific actions to be taken.

5 STUDY PROCEDURES

5.1 Patient Numbering

Every patient that gives informed consent will be logged and allocated a unique patient identification number. The unique patient identification number will consist of 9 digits (2 for the study number, 2 for the country, 2 for the site number and 3 for patient number), will be

assigned sequentially to each patient within each site and will identify the patient throughout the study.

5.2 Screening Failures

Screening failures are defined as patients who have given informed consent for the study, but who have not met the study Inclusion and/or the Exclusion Criteria. Re-screening of patients will be at the discretion of the Medical Monitor. If a patient is re-screened, they will be given a new patient identification number and must give informed consent again.

5.3 Study Visits

5.3.1 Pre-Treatment

The following assessments should be performed on Day 0 prior to the first dose preferably in the following order:

- Informed consent
- Inclusion/exclusion criteria
- Medical history
- COVID-19 infection history (SARS-CoV-2 variant information to also be collected if available)
- Patient demographics
- Physical examination (chest examination only unless a physical examination is deemed necessary by the Investigator)*
- WHO OSCI*
- Height and weight
- Vital signs (to include temperature, respiratory rate, heart rate and blood pressure)*
- BCSS
- NEWS2 (the highest NEWS2 score for each calendar day should be collected)
- EQ-5D-5L (complete questionnaire)
- Height and weight
- Urine pregnancy test, if applicable
- Check the patient will be able to use the nebuliser
- Randomisation
- Blood sample for immunogenicity test (all sites/patients, where collection is feasible)
- Recording of AEs, SAEs and concomitant medications

*Physical examination, WHO OSCi, and vital signs assessments should be conducted together at approximately the same time each day.

Eligibility to enter the study may be aided with data captured from SOC procedures and tests performed as part of the admission process.

Patients may take the first dose of study medication either on the same day as the pre-treatment assessments or the next day depending on timings. Day 1 is the day the first dose of study medication is taken. If Day 1 is the same as the day the pre-treatment assessments are performed then the Day 1 assessments do not need to be repeated.

5.3.2 Days 1 to 14

The following assessments should be performed daily from Day 1 to 14.

For patients that remain in hospital the following assessments should be performed preferably in the following order:

- WHO OSCI*
- Physical examination (chest examination only unless a physical examination is deemed necessary by the Investigator)*
- Vital signs (to include daily temperature, respiratory rate, heart rate and blood pressure)*
- BCSS
- EQ-5D-5L (complete questionnaire on Day 7 only. Mobility, self-care and usual activities dimensions from Day 1 to Day 14)
- COVID-19 symptom assessment
- NEWS2 (the highest NEWS2 score for each calendar day should be collected)
- Device training (if required)
- Administration of study medication
- Recording of AEs, SAEs and concomitant medications.

*Physical examination, WHO OSCI, and vital signs assessments should be conducted together at approximately the same time each day.

1

CCI

- CCI [REDACTED]
- CCI [REDACTED]
- CCI [REDACTED]

For patients who have been discharged from hospital the following should be conducted over telephone/video call preferably in the following order:

- WHO OSCi
- BCSS
- EQ-5D-5L (complete questionnaire on Day 7 only. Mobility, self-care and usual activities dimensions from Day 1 to Day 14)
- COVID-19 symptom assessment
- Device training (if required)
- Administration of study medication
- Recording of AEs, SAEs and concomitant medications

If the patient has discontinued dosing and consents to data collection, attempts should be made to collect the following key data:

- WHO OSCi
- BCSS
- EQ-5D-5L (complete questionnaire on Day 7 only. Mobility, self-care and usual activities dimensions from Day 1 to Day 14)
- COVID-19 symptom assessment
- Recording of AEs, SAEs and concomitant medications

5.3.3 End of Treatment

These assessments should be performed on Day 15 (see Sections 4.3.1 and 5.5).

For patients that remain in hospital the following assessments should be performed, preferably in the following order:

- WHO OSCi*
- Physical examination (chest examination only unless a physical examination is deemed necessary by the Investigator)*
- Vital signs*
- BCSS
- EQ-5D-5L (complete questionnaire)
- COVID-19 symptom assessment
- Long-COVID-19 assessment
- NEWS2 (the highest NEWS2 score for each calendar day should be collected)

- Recording of AEs, SAEs and concomitant medications.

*Physical examination, WHO OSCi, and vital signs assessments should be conducted together at approximately the same time each day.

For patients who have been discharged from hospital the following should be conducted over telephone/video call preferably in the following order:

- WHO OSCi
- BCSS
- EQ-5D-5L (complete questionnaire)
- COVID-19 symptom assessment
- Long-COVID-19 assessment
- Recording of AEs, SAEs and concomitant medications.

5.3.4 Follow-up

All follow-up assessments can be either done face-to-face if the patient remains in hospital or via telephone/video call if the patient has been discharged from hospital as per the study schedule.

Days 16 to 28

WHO OSCi, BCSS, the mobility, self-care and usual activities dimensions of EQ-5D-5L, NEWS2, COVID-19 symptoms, AEs, SAEs, and concomitant medications should continue to be collected on a daily basis from the patient. In addition, the EQ-5D-5L (complete questionnaire) should be completed and long- COVID-19 assessment should be performed on Day 28. For patients who have been discharged, assessments should be performed via telephone/video link, if possible.

NEWS2 will only be assessed if the patient remains in hospital. If the patient has been discharged from hospital NEWS2 will not be assessed. For hospitalised patients, if the components of NEWS2 have already been assessed on the day of the visit, this data can be used on the study to avoid the same procedures being conducted twice. The highest NEWS2 score for each calendar day should be collected.

Days 29 to 35

WHO OSCI, COVID-19 symptoms, the mobility, self-care and usual activities dimensions of EQ-5D-5L, AEs, SAEs, and concomitant medications should continue to be collected (as per Sections 7.7.1 and 7.7.2) on a daily basis until (and including) Day 35.

Days 36 to 90

Blood sample for immunogenicity testing should be obtained from the patient (all sites/patients, where collection is feasible) on Day 44 (+/- 5 days).

Updates to ongoing AEs and SAEs will be collected at Days 44, 60, and 90, and at any unscheduled study visits during this period as per Section 7.7.1 and 7.7.2.

New AEs and SAEs will be collected up to 28 days after the last dose of study medication and documented at the next scheduled or unscheduled study visits as per Section 7.7.1 and 7.7.2.

All concomitant medications will continue to be recorded until study completion.

In addition, BCSS, EQ-5D-5L (complete questionnaire), COVID-19 symptoms and long-COVID-19 assessments should be performed on Day 60 (-2 to +5 days) and Day 90 (-2 to +5 days).

5.4 Unscheduled Visits

The Investigator can request any of the study procedures described in the study schedule to be repeated as extra follow-up visits or to be added to a study visit where necessary. Unscheduled visits may be necessary if the patient is experiencing prolonged symptoms which the Investigator feels could be related to their study medication or if the Investigator is concerned about the patient's health. Unscheduled visits/study procedures should be captured in the source documents.

5.5 Patient Withdrawal

Patients may withdraw from the study at any time at their own request. If a patient does not return for a scheduled visit, every effort should be made to contact the patient. In any circumstance, every effort should be made to document patient outcome, if possible. The Investigator should enquire about the reason for withdrawal, request that the patient disposes of all unused study medication (as instructed) and request the patient undergoes a final visit, if applicable, and follow-up with the patient regarding any unresolved AEs.

Please refer to Section 4.3.1 for individual patient stopping rules.

If patient is withdrawn from the study or from the study medication, the reason for withdrawal will be documented in the source documents. If the patient is withdrawn from taking the study medication only but continues to give consent for data to be collected, the study schedule should be followed until Day 90.

Lost to follow-up:

Patients will be considered as lost to follow-up if no contact is made with the patient for at least 5 consecutive visits up to and including the Day 35 visit. A patient would also be considered lost to follow-up if no contact is made with the patient after the Day 35 visit and contact cannot be re-established up to and including the Day 90 visit. However, since maximum data collection for all patients is important to support the analyses of study endpoints, continued attempts to contact patients lost to follow-up should be made to allow completion of the follow-up assessments, wherever possible, up to the scheduled Day 90 visit. The status of 'lost to follow-up' should be amended in the CRF if patient contact is re-established and additional study follow-up data can be obtained.

For further guidance, see Appendix B.

6 STUDY ASSESSMENTS

6.1 Informed Consent

Informed consent will be obtained from the patient after the study has been fully explained and the patient has been given ample time to consider the study and discuss it in detail. The method of obtaining consent may vary due to the nature of this study. The method of obtaining and documenting the informed consent and the contents of the consent will comply with International Conference on Harmonisation Guideline for Good Clinical Practice (ICH GCP), and all applicable laws and regulations. Different methods, including written, verbal or electronic consent may be used. Each method will be discussed and approved by the Sponsor (or delegate) before the site takes the first consent. Whichever method is used informed consent will always be obtained from the patient prior to any study related procedures being performed. Informed consent must be obtained by a qualified medical doctor or nurse who have received study training.

If there is a new version of the patient information sheet and informed consent form, patients will be reconsented at their next study visit or, if they were already discharged from the hospital, they may be reconsented verbally over the phone/video link, or electronically. Patients will be informed as soon as possible of the changes and the Sponsor will determine whether the patients need to visit the site prior to their next study visit.

6.2 Medical History

The patient's medical history will be recorded in the source documents by the Investigator or their delegate to ensure the patient's eligibility.

The medical history should include, but is not limited to;

- Significant current and past medical history in the last 5 years, including hospitalisations, operations and medical history that affects inclusion and exclusion criteria (including sterilisation and contraception).
- Social history regarding smoking habits, alcohol consumption, drug allergies and medication use.
- For women, a menstrual history and history of contraception (if applicable).
- Vaccinations within 6 months prior to randomisation.

6.3 COVID-19 Infection History

The patient's COVID-19 infection history will be recorded in the source documents by a medical doctor or qualified nurse from the study team. Information regarding symptoms in the preceding 24 hours will be recorded.

A checklist/worksheet will be provided to study site staff to outline and help document the minimum symptoms to be assessed.

In addition, SARS-CoV-2 variant information will be collected (if available).

6.4 Patient Demography

Patient demographics will be recorded in the source documents. These will include age, sex, race/ethnicity and residence in care home, unless local laws or regulations do not permit this.

6.5 Physical Examination

A physical examination will be performed by a medical doctor on Day 0 or Day 1 prior to the first dose as per the study schedule.

Physical examinations may be repeated at various time points throughout the study, as clinically indicated.

If sites have difficulty in completing the chest examination due to risk of contamination/local policies, this will not be considered a protocol deviation, but will need to be explained in a file note. Height and weight will be recorded pre-treatment.

A checklist/worksheet will be available to study site staff to provide guidance on the physical examination. Results of the examinations will be recorded in the source documents.

6.6 Ordinal Scale for Clinical Improvement

The OSCI to be used in this trial is the 18 February 2020 version as recommended by the WHO (7).

Ordinal Scale for Clinical Improvement

Patient State	Descriptor	Score
Uninfected	No clinical or virological evidence of infection	0
Ambulatory	No limitation of activities	1
	Limitation of activities	2
Hospitalised	Hospitalised, no oxygen therapy	3
	Oxygen by mask or nasal prongs	4
Hospitalised	Non-invasive ventilation or high-flow oxygen	5
	Intubation and mechanical ventilation	6
	Ventilation + additional organ support – pressors, RRT, ECMO	7
Dead	Death	8

RRT – renal replacement therapy; ECMO - extracorporeal membrane oxygenation

The assessment should be carried out once a day at approximately the same time each day from Pre-treatment until Day 35. It is recommended that this assessment should be carried out by a clinically qualified member of the study team, i.e. a medical doctor or a qualified nurse. The assessment may be carried out face to face (before discharge) or over the phone/video link (post-discharge).

Patients' status on the day of hospital discharge should be assessed as ambulatory/uninfected (WHO OSCI score of 0, 1 or 2).

On the day of hospital discharge and on the days following hospital discharge, patients should be asked the following questions about their clinical status and return to the pre-COVID-19 level of activity:

- “In the past 24 hours, did you experience any signs or symptoms of your coronavirus infection?” “Yes” or “No” answer will be required.
- “In the past 24 hours, did you feel that your usual activities (e.g. work, study, housework, family or leisure activities) have returned to the level from before your coronavirus infection and did not require additional assistance/support*?” “Yes” or “No” answer will be required.

* assistance/support is defined as additional help of other people and/or requirement for supplemental oxygen (or a higher level of supplemental oxygen), compared to the pre-COVID-19 state.

In order to minimise any potential influence on the patients, the interviewers will be required to read the questions to patients verbatim and not to change or interpret them in any way. The following scoring algorithm will be applied:

Presence of signs/symptoms of coronavirus infection (or virological evidence of infection)?	Usual activities returned to baseline level?	WHO OSCI score
No	Yes	0
Yes	Yes	1
No	No	2
Yes	No	2

The result of the OSCI assessment, from the day of hospital discharge, must be based upon the patient's responses to the 2 questions specified above and must not be adjusted based on the results from other outcome assessments (e.g. BCSS, brief pain inventory, long COVID-19 symptom assessment, and EQ-5D-5L), even if these data provide conflicting clinical information.

Repeated assessments of virological clearance in patients discharged from the hospital are not feasible within the study. Patients discharged from the hospital will be considered to have no virological evidence of infection unless a positive test is obtained.

The applicable WHO OSCI score and the date of assessment should be recorded in the source documents.

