8.5.1 Analysis of the Primary Efficacy Endpoint

The same method of analysis will be used for both primary endpoints. The primary analysis will use a Cox proportional hazards model. Time to hospital discharge and time to recovery will be determined using data collected up to Day 28 only. WHO OSCI data collected after Day 28 will only be used to assess relapse for patients who were discharged or recovered prior to Day 28. Relapse will be defined as a WHO OSCI score of >2 for hospital discharge and a WHO OSCI score of >1 for recovery. Patients who die will be administratively censored at Day 28, i.e. time to hospital discharge and time to recovery will be fixed at 28 days for these patients. Patients who neither recover nor die will be censored at the date of their last WHO OSCI assessment where discharge/recovery was not possible. Covariates will be included for treatment arm, age (as a continuous variable), sex, and Country/Region. Further covariates

may be defined in the SAP. The hazard ratio for recovery of SNG001 versus placebo, 95% confidence intervals (CI) and p-value will be presented.

Ties in event times will be handled using the exact method, or the Efron approximation if computational difficulties arise.

In addition, Kaplan-Meier estimates of time to hospital discharge and time to recovery for 25%, 50% (median time) and 75% of patients will be presented.

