#### 5.3.1 Derivations from the Ordinal Scale for Clinical Improvement

##### 5.3.1.1 Hospital Discharge

Hospital discharge will be defined as the first post baseline score of  $\leq 2$  which is sustained for a minimum of 7 days and up to the date of the Day 35 assessment or study withdrawal, whichever occurs first (see [Section 15](#) for changes from the protocol) according to the WHO 9-point Ordinal Scale for Clinical Improvement (OSCI)[1]. If any OSCI assessments are missing following discharge, sustained hospital discharge will be confirmed by the subject's location on the assessment day, which will be recorded in the CRF as "In Hospital" or "Not in Hospital" and may be entered retrospectively. If location is missing, the patient will be assumed to be not in hospital under the assumption that any hospitalisations prior to the last completed assessment will be recorded in the clinical database. This will not include assessments missing following study withdrawal if study withdrawal occurs within 7 days of hospital discharge. If a patient withdraws from the study within 7 days of hospital discharge, they will not be considered as discharged. Hospital discharge will be derived for all scheduled post-baseline assessments up to day 28.

Time to hospital discharge (in days) for discharged patient will be calculated as the following:

$$\text{Date of first hospital discharge} - \text{date of randomisation} + 1$$

Because OSCI score is collected up to day 35, the latest possible hospital discharge date will be at the Day 28 assessment (because it must be sustained for a minimum of 7 days). Patients who die will be administratively censored at the maximum time to hospital discharge. Patients who are not discharged for a minimum of 7 days will be considered censored at the date of their last OSCI assessment of 3 or above. Time to censoring will be calculated as the following:

Date of last OSCi assessment >2 on or before Day 28 – date of randomisation + 1.

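### Protocol 6.6 scores every day from first discharge with two questions that return only 0 to 2, so a readmitted patient who answers them can count as discharged without rebound

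*Protocol*

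**What the plan says.** **Who is asked, and when.** Protocol 6.6: "On the day of hospital discharge and on the days following hospital discharge, patients should be asked the following questions". There are two yes/no questions, one on symptoms and one on return to usual activities without extra support.

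**How the answers become a score.** "The following scoring algorithm will be applied", followed by a table of the four answer combinations with scores 0, 1, 2 and 2. The same section makes the result binding: the OSCI result, "from the day of hospital discharge, must be based upon the patient's responses to the 2 questions specified above". It also forbids adjusting that result from other outcome assessments such as the BCSS or EQ-5D-5L.

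**The scale itself.** Also in Protocol 6.6, levels 3 to 7 belong to hospitalised patients. Level 3 is "Hospitalised, no oxygen therapy" and level 4 is oxygen by mask or nasal prongs.

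**How loss of discharge is detected.** Protocol 8.5.1: "Relapse will be defined as a WHO OSCI score of >2 for hospital discharge", and "a WHO OSCI score of >1 for recovery". SAP 5.3.1.1 requires a score of 2 or below, sustained for at least 7 days and up to Day 35 or withdrawal. Its only use of location is for gaps: "If any OSCI assessments are missing following discharge, sustained hospital discharge will be confirmed by the subject's location on the assessment day".

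**Key secondary endpoints.** SAP 5.3.1.3 and 5.3.1.4 derive progression from any post-baseline OSCI of at least 5 or at least 6 up to Day 35.

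**The concern.** Discharge without rebound is one of two primary endpoints, and the trial succeeds if either is significant. The rebound condition is there so that a treatment which empties beds sooner but sends more patients back gets no credit for those discharges. If the score that must signal a rebound comes from a table that stops at 2, the condition does nothing for readmitted patients who answer the questions.

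The instruction also clashes with the scale printed beside it, so sites may resolve it differently. Some will record 2 for a readmitted patient and others 3 to 7, and the primary endpoint then means different things at different sites.

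The same scoring feeds the first two key secondary endpoints. A non-fatal spell at level 5 or above during a readmission could go unrecorded there as well.

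**Working it through.** **Step 1: what the algorithm can return.**

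| Symptoms present? | Usual activities back? | Score | Above 1 (recovery relapse)? | Above 2 (discharge relapse)? |
|---|---|---|---|---|
| No | Yes | 0 | No | No |
| Yes | Yes | 1 | No | No |
| No | No | 2 | Yes | No |
| Yes | No | 2 | Yes | No |

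The rebound test can work for recovery. From the two questions alone it cannot work for discharge.

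**Step 2: a readmitted patient on mask oxygen who can answer.** The footnote to the second question counts as support a "requirement for supplemental oxygen (or a higher level of supplemental oxygen), compared to the pre-COVID-19 state". The answer is therefore No and the score 2. The scale in the same section gives this patient 4. With 2 recorded, the OSCI is not missing, SAP 5.3.1.1 does not consult location, and the first discharge date stands as an event.

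**Step 3: events at stake.** Inputs from Protocol 8.1: 305 per arm, 70% placebo discharge at Day 28, hazard ratio (HR) 1.45, 25% exponential dropout by Day 28. (SAP Section 6 opens with the same HR; its simulation text uses others, which I do not use here.) With 28-day cumulative hazards a for discharge and w for dropout, expected events per arm = 305 × a/(a + w) × (1 − exp(−(a + w))).

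- w = ln(100/75) = 0.2877.
- Placebo: a = ln(100/30) = 1.2040; 305 × 0.8071 × 0.7750 = 190.8.
- SNG001: a = 1.45 × 1.2040 = 1.7458; 305 × 0.8585 × 0.8691 = 227.6.
- Total 418.4.

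The documents give no readmission rate. If 5%, 10% or 15% of discharged patients in both arms were readmitted and not discharged again by Day 28, about 21, 42 or 63 events would be counted wrongly (0.05, 0.10 or 0.15 × 418.4).

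**Step 4: effect on the hazard ratio.** Simulation with the same inputs: exponential times in whole days, Cox model with Efron ties. Readmitted patients are either kept as events at first discharge (literal rule) or treated as never discharged and censored at Day 28. The standard error (SE) of the log HR is about 2/√418.4 = 0.098.

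| Assumed readmission, placebo / SNG001 | HR, literal rule | HR, readmission as rebound | Difference in SE |
|---|---|---|---|
| 5% / 5% | 1.46 | 1.42 | 0.2 to 0.3 |
| 10% / 10% | 1.46 | 1.39 | 0.5 |
| 3% / 6% | 1.45 | 1.34 | 0.8 |
| 5% / 10% | 1.46 | 1.28 | 1.3 |

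With no true effect and equal readmission there is no bias. With no true effect and 5% v 10%, the HR is about 1.00 instead of 0.92.

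These are upper-end figures. If instead 80% of readmitted patients are discharged again after a mean stay of about 7 days (also an assumption), the gap roughly halves: 5% / 10% gives 1.46 v 1.36 (0.7 SE), 3% / 6% gives 1.45 v 1.40 (0.3 SE), and 5% / 5% gives 1.46 v 1.45 (0.1 SE).

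**Step 5: direction.** The error need not favour SNG001. If placebo had the higher rate (10% v 5%), simple scaling of events gives 1.45 × 0.95/0.90 = 1.53 with readmission counted, so the literal rule would understate the benefit.

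**The case against.** A reader might infer that no score above 2 can be recorded after discharge, that every readmitted patient counts as discharged, or that the endpoint is simply time to first discharge. The documents do not support that.

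- Protocol 6.6 prints the whole scale with 3 to 7 for inpatients, and links telephone or video assessment to the period after discharge. Its ban on adjustment concerns other outcome assessments, not hospital status. Protocol 8.5.1 presupposes that scores above 2 occur after discharge. A site could reasonably score a readmitted patient 3 to 7.
- Death is captured: SAP 7.3.1.1 sets missing scores to 8 from the date of death.
- A readmitted patient too ill to answer has a missing OSCI, which triggers the location check in SAP 5.3.1.1.
- SAP 9.1.1.3 plans a sensitivity analysis that defines discharge by absence of readmission within 7 days, so readmission was meant to count.
- The facts should mostly be in the database. SAP 5.3.1.1 assumes hospitalisations are recorded, and Protocol 7.3 makes an adverse event that requires inpatient hospitalisation serious.
- SAP Section 6 labels the 70% placebo rate as sustained discharge, so removing readmissions from it partly double-counts, and nothing in the documents suggests that SNG001 raises readmission.

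All of this stands, and it limits the point. It does not remove it. The scoring instruction is worded as a must, has no readmission exception, and leaves a site that follows it with a recorded score of 2. The sensitivity analysis covers only 7 days, does not name its data source and leaves the primary analysis unchanged. The location check belongs to the discharge derivation only; SAP 5.3.1.3 and 5.3.1.4 have no equivalent.

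**Conclusion.** The passages contradict each other for one group: patients readmitted after first discharge who are able to answer the two questions. For them the stated scoring rule leads to a wrong result on a primary endpoint, or to a result that depends on how the site read the rule. Deaths and patients unable to answer are handled for the discharge endpoint. Rebound for the recovery endpoint is reachable from the two questions. For the first two key secondary endpoints, a non-fatal score of 5 or above during a readmission could be missed; the endpoint of death alone is not affected.

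The size cannot be derived from the documents, because they give no readmission rate. On assumed rates it is small when readmission is low and balanced (up to about 0.5 SE at 10% in each arm). It reaches about 1.3 SE only if SNG001 doubles readmission from 5% to 10% and no readmitted patient is stably discharged again by Day 28. A reader might infer that the treatment effect is inflated; the documents do not show that, and the direction depends on which arm readmits more. The change should still be made, because unequal readmission is what the no-rebound condition is there to detect.

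**What to change.** **SAP 5.3.1.1.** Count as rebound any day after the day of discharge on which the CRF location, or a recorded hospitalisation, shows the patient in hospital, whatever OSCI score is recorded. The discharge day itself must be left out, since the patient may be logged in hospital that day while Protocol 6.6 asks for a score of 0 to 2. Apply the same rule to the censoring date in that section. It uses the last OSCI above 2, and would otherwise censor a readmitted patient scored 2 at a date before the first discharge.

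**Protocol 6.6 or the site scoring guide.** State that the two-question algorithm applies on the day of discharge and on later days out of hospital, and that readmitted days are scored on the hospitalised levels of the scale. This also protects the key secondary endpoints, which the SAP sentence alone does not.

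**Cost.** One or two SAP sentences and one clarifying sentence for sites. The location field already exists and may be completed retrospectively. The downside is that location must be filled in for all post-discharge days, not only those with a missing OSCI, because the SAP treats a missing location as not in hospital.
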